2. STUDY OBJECTIVES AND ENDPOINTS

2.1. Objectives

2.1.1. Primary objectives

- To determine the effect of CC-4047 and prednisone in the treatment of Primary, Post Polycythemia Vera, or Post Essential Thrombocythemia Myelofibrosis (PMF, post-PV MF, or post-ET MF).
- To determine the safety of CC-4047 and prednisone in the treatment of Primary, Post Polycythemia Vera, or Post Essential Thrombocythemia Myelofibrosis (PMF, post-PV MF, or post- ET MF).

2.1.2 Secondary study objectives

• To further explore the nature and quality of responses to CC-4047 and prednisone

2.2. Endpoints

2.2.1. Primary Endpoint

- Best overall response as determined by International Working Group Criteria over the first 6 cycles (168 days) of study treatment
- Safety (type, frequency, severity [National Cancer Institute (NCI) Common Terminology Criteria for Adverse Events (CTCAE) version 3.0] of adverse events (AEs), and relationship of AEs to CC-4047)

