There is previous human experience with the treatment of MMM by the original IMiD, thalidomide. Single-agent thalidomide at "conventional" doses (> 100 mg/d) has been evaluated in MMM based on its antiangiogenic properties and the prominent neoangiogenesis that occurs in MMM. Thalidomide monotherapy at such doses produces approximately a 20% response rate in anemia but is poorly tolerated (an adverse dropout rate of >50% in 3 months). To improve efficacy and tolerability, 21 symptomatic subjects (hemoglobin level < 10 g/dL or symptomatic splenomegaly) with MMM were treated with low-dose thalidomide (50 mg/d) along with a 3-month oral prednisone taper (beginning at 0.5 mg/kg/d). The combination therapy was well tolerated in all enrolled subjects, with 20 subjects (95%) able to complete 3 months of treatment. An objective clinical response was demonstrated in 13 (62%) subjects, all improvements in anemia. Among 10 subjects who were transfusion dependent, 7 (70%) improved and 4 (40%) became transfusion independent. Improvements in anemia correlated with lower pretherapy CD34⁺cell counts in the peripheral blood (median, 81.2 CD34+ cells/μL versus 554 CD34⁺ cells/ μ L [nonresponders]; P = 0.03) as well as lower numbers of circulating blasts (median, 0.8% versus 4.7% in nonresponders; P = 0.03). Among 8 subjects with thrombocytopenia (platelet count <100 x 10⁹/L), 6 (75%) experienced a 50% or higher increase in their platelet count. In 4 of 21 subjects (19%), spleen size decreased by more than 50%. Responses observed were mostly durable after discontinuation of the prednisone. The dose of thalidomide in this study (50 mg/d) was better tolerated than the higher doses used in previous studies. Adverse events associated with corticosteroid therapy were mild and transient. Clinical responses did not correlate with improvements in either intramedullary fibrosis or angiogenesis. The thalidomideprednisone combination was well tolerated and appeared to be a promising drug regimen for treating cytopenias in subjects with MMM.

Ten of the MMM subjects completed an additional 3 month thalidomide-only treatment phase of the study. After discontinuation of the prednisone, clinical responses were maintained in 62% in terms of anemia, 66% in terms of thrombocytopenia, and 50% of the splenomegaly responses. (Mesa, 2003)

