3. INVESTIGATIONAL PLAN

3.1. Overall design

CC-4047 is a phase 2, prospective, open-label study to determine the efficacy and safety of CC-4047 at a 0.5 mg dose, in combination with prednisone, to study further in subjects with primary, post polycythemia vera, or post essential thrombocythemia myelofibrosis

Screening:

Potential subjects will enter screening and be evaluated for the inclusion and exclusion criteria for the Treatment Period of this study. The screening period will not last more than 28 days. The assessments and procedures that will be performed during screening are outlined in Appendix M: Schedule of Events. Screening assessments will include an informed consent, medical history, review of prior medications, complete physical exam, ECOG performance status assessment, complete blood count (CBC) with differential, serum chemistries, urinalysis, thyroid function tests, 12-lead ECG, bone marrow biopsy and aspirate to confirm diagnosis and for standard cytogenetics, JAK2 mutation (by quantitative polymerase chain reaction [PCR], and PCR or fluorescent in situ hybridization (FISH) for bcr/abl, spleen and/or liver (if spleen is absent) measurements, and QoL Assessments.

Females of reproductive potential¹ must adhere to the scheduled pregnancy testing as required in the POMALYST REMSTM program. All study participants must be registered into the mandatory POMALYST REMSTM program, and be willing and able to comply with the requirements of the POMALYST REMSTM program.

Before starting study drug:

Subjects must follow pregnancy testing requirements as outlined in the POMALYST REMS TM program.

Treatment Period:

Subjects meeting all inclusion and exclusion criteria will receive 0.5mg CC-4047. Prednisone will be given during first 3 cycles of therapy. It will be dosed orally at the dose of 30 mg/day during cycle 1, 15 mg/day during cycle 2, and 15 mg every other day during cycle 3, and then it will be discontinued. Prednisone will be used from commercially available supplies.

Subjects will remain on study treatment in the Treatment Period in the absence of disease progression or toxicity warranting discontinuation of therapy. Twenty-eight days is considered one cycle of therapy. Subjects may be taken off study at 6 months if there is no response, however, they should continue to be followed until disease progression or initiation of an alternate therapy.

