3.5.2. Dosing regimen

Initial dosing of CC-4047 for eligible subjects will be 0.5mg daily. Subjects will receive oral CC-4047 from day 1 through day 28, continuously, in the absence of disease progression or toxicity warranting discontinuation of therapy. Twenty-eight days is considered one cycle of therapy. Dosing will be at approximately the same time each day. CC-4047 capsules should be swallowed whole, and should not be broken, chewed or opened. CC-4047 should be taken without food, at least 2 hours before or 2 hours after a meal. If a dose of CC-4047 is missed, it should be taken as soon as possible on the same day. If it is missed for the entire day, it should not be made up, rather it should be taken at the next scheduled time point. Patients who take more than the prescribed dose of CC-4047 should be instructed to seek emergency medical care if needed and contact study staff immediately.

Only one cycle of study drug will be supplied to the subject each cycle. Prednisone will be given during first 3 cycles of therapy. It will be dosed orally at the dose of 30 mg/day during cycle 1, 15 mg/day during cycle 2, and 15 mg every other day during cycle 3, and then it will be discontinued.

Subjects must also receive oral low-dose aspirin (81 mg) as prophylactic anti-thrombotic treatment unless it is contraindicated or the subject has a platelet count less than $75,000/\mu L$. If low-dose aspirin is contraindicated, the investigator should prescribe another appropriate prophylactic anti-thrombotic therapy.

Single oral CC-4047 doses of 1 and 50 mg in healthy adult males were safe and resulted in Cmax values of 11.2 and 288 ng/mL respectively. Given the short half-life in healthy adult male humans (approximately 8 to 11 hours) and once daily dosing, minimal accumulation is expected. A daily dosing schedule will be utilized for this study.

Subjects experiencing adverse events may need study treatment modifications (Table 1).

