5.3 Statistical Methodology

5.3.1. Primary Endpoint

The primary endpoint of this trial is best overall response. An evaluable subject will be classified as a treatment success for the primary endpoint if the subject's best overall response is CR, PR or CI (Clinical Improvement) as determined by International Working Group Criteria over the first 6 cycles of study treatment at 0.5mg/day dose. The largest success proportion where the proposed treatment regimen would be considered unpromising in this population is 5%, representing the probability of a response by chance. The smallest success proportion that would warrant further subsequent studies with the proposed treatment regimen in this subject population is 20%.

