5.3.3. Analysis Plan

Primary Endpoint

The observed response rate over the first 6 cycles of therapy at 0.5mg/day will be estimated by the number of responses (confirmed CR, PR or CI) over the first 6 cycles divided by the total number of evaluable subjects. Confidence intervals for the true response rates will be calculated according to the approach of Duffy and Santner.

Secondary Endpoints

Duration of response: duration of response is defined as the date at which the subject's objective status is first noted to be a CR, PR or CI to the date progression is documented (if one has occurred) or to the date of last follow-up (for those subjects who have not progressed).

Time to response: The time to response is defined as the time from study registration to the first date at which the subject's objective status was classified as a response (CR, PR or CI). In subjects who do not achieve a response, time to response will be censored at the subject's last evaluation date. The distribution for each of these event-time variables (duration of response and time to response) will be estimated by Kaplan-Meier curves.

Best overall response as determined by the International Working Group Criteria over the first 12 cycles of study treatment: will be estimated by the number of responses (confirmed CR, PR or CI) over the first 12 cycles divided by the total number of evaluable subjects. Confidence intervals for the true response rates will be calculated according to the approach of Duffy and Santner.

Cytogenetic responses and molecular response: cytogenetic responses and molecular responses will be summarized as well as evaluated graphically. Correlations among clinical responses and laboratory variables will be explored using a Wilcoxon/Kruskal-Wallis test for ordered contingency tables. Mutation status will be explored in relation to clinical outcome (response) using Fisher's exact test.

Quality of Life (QOL) assessments: For each of the QOL assessment components, changes from baseline to each of the follow-up time points will be reported. The change will be compared between two subgroups: subjects who response to the treatment and subjects who do not response. Normality testing via the Shapiro-Wilk procedure will determine whether or not parametric or nonparametric procedures will from the basis for analysis (two-sample t-test, Wilcoxon rank sum test).

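### The primary endpoint counts responses met during the three-cycle prednisone taper even if later lost, and no planned summary shows how many successes persist off prednisone

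*Combined protocol and SAP*

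**What the plan says.** Section 2.2.1 sets the primary efficacy endpoint as "Best overall response as determined by International Working Group Criteria over the first 6 cycles (168 days) of study treatment". Section 5.3.1 classes a subject as a success "if the subject's best overall response is CR, PR or CI (Clinical Improvement) as determined by International Working Group Criteria over the first 6 cycles". Section 5.3.3 estimates the rate as "the number of responses (confirmed CR, PR or CI) over the first 6 cycles divided by the total number of evaluable subjects". The requirement of confirmation appears there without an interval or minimum duration. The IWG criteria are cited but not reproduced.

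On treatment, section 3.1 says "Prednisone will be given during first 3 cycles of therapy", after which it stops. Section 3.5.2 adds "Twenty-eight days is considered one cycle of therapy". CC-4047 itself continues for as long as the treating physician sees benefit (3.8).

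The go rule uses the success count alone: at least 2 of 20 to continue (5.5) and at least 4 of 37 to call the regimen promising (5.3.2). Section 5.3.3 also plans Kaplan-Meier curves for time to response and duration of response, and a 12-cycle best-response rate. Duration runs from first response to documented progression, or to last follow-up if there is none.

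**The concern.** Half of the assessment window is on prednisone and half is off it. Best response looks back over the whole window, so a subject who responds in cycle 2 and has lost the response by cycle 5 counts the same as one still responding at the end of cycle 6. After cycle 3 the regimen is CC-4047 alone for as long as it helps. Whether responses carry into that phase is a basic part of the secondary objective on the nature and quality of responses (2.1.2).

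The trial should have the information to show this, but the plan does not ask for it. A favourable result could be reported with no statement of how many responses were still present about 12 weeks after the steroid ended.

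**Working it through.** **1. The plan's own figures.** Take X1 as binomial(20, p) and X2 as binomial(17, p). The trial stops early if X1 ≤ 1, and P(go) is the sum over x = 2 to 20 of P(X1 = x) × P(X2 ≥ 4 − x).

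| True rate | P(go), computed | P(go), section 5.6 | Stop at stage I, computed | Stop at stage I, section 5.6 |
|---|---|---|---|---|
| 5% | 0.090 | 0.09 | 0.736 | 0.74 |
| 10% | 0.439 | 0.44 | 0.392 | 0.39 |
| 15% | 0.751 | 0.75 | 0.176 | 0.18 |
| 20% | 0.910 | 0.91 | 0.069 | 0.07 |
| 25% | 0.971 | 0.97 | 0.024 | 0.02 |

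The design arithmetic is correct. The question is only what a success conveys.

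**2. Overlap of window and taper.** 6 × 28 = 168 days in the window; 3 × 28 = 84 days on prednisone; 168 − 84 = 84 days off it.

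**3. What each planned summary can show.**
- The 6-cycle and 12-cycle rates are both best responses. Neither falls when a response is lost.
- Time to response records only the first response.
- Duration of response has progression as its only event. A subject who loses a response without documented progression, stops for lack of effect (3.8) and leaves follow-up on starting another therapy (3.9) would be censored as if still responding. This holds for the definition as written. The documents do not say whether the IWG definition of progression includes loss of response; if it does, this part of the gap narrows.

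**4. What the background says about persistence (section 1.2).**
- Thalidomide plus prednisone, 21 subjects: "After discontinuation of the prednisone, clinical responses were maintained in 62% in terms of anemia". The figure for spleen responses is 50%. The same account describes the responses as mostly lasting after prednisone ended, and gives no denominators for these percentages.
- Randomized pomalidomide study, prednisone tapered over three cycles: responses to pomalidomide with or without prednisone lasted 3.2 to 16.9+ months. 3.2 months is 3.2 × 28 ≈ 90 days or 3.2 × 30.4 ≈ 97 days.
- Lenalidomide plus prednisone, same prednisone schedule: responses lasted 4.1 to 20 months, median 15. 4.1 months is about 115 to 125 days. Median time to response was 12 weeks, which is 84 days.

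Both minimum durations exceed 84 days, so none of those reported responses was confined to a taper. They do not settle status at day 168: a 97-day response that began by day 56 would end by day 56 + 97 = 153.

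**5. Illustration of size.** Rate still responding = best-response rate × share kept.
- 62% kept: 0.20 × 0.62 = 0.124. In 37 subjects, 7.4 expected successes, of which 4.6 are still responding.
- 80% kept: 0.20 × 0.80 = 0.16, or 5.9 of 7.4.

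The 62% is borrowed from another drug and is low if applied to every success, because a response first met after prednisone ends cannot be lost to its withdrawal. If half the successes arise after the taper (an assumption suggested by the 12-week median), the share kept is 0.5 + 0.5 × 0.62 = 0.81, close to the upper value.

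**6. Why the decision rule should not be redefined.** If only persisting responses counted and the boundaries stayed the same, P(go) would fall from 0.91 at 20% to 0.61 at 12.4% and 0.79 at 16%. The target rate or the sample size would have to be restated.

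**The case against.** The strongest reply is that the nearest precedents are reassuring. The pomalidomide study and the lenalidomide-prednisone study both report shortest responses longer than the taper, and even the thalidomide report is favourable overall. The 62% comes from a small study of a different drug. Only ten of its subjects completed the later thalidomide-only phase, so some of the responses not maintained may reflect non-completion rather than relapse. All of this stands, and it is why the size above is only an illustration.

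Best response also matches the combination objective (2.1.1), and confirmation excludes the briefest responses. This stands too. But with no interval stated, a response confirmed within the 84 days could still be lost afterwards.

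It can also be said that duration of response already covers persistence. It does so only in part, because loss without documented progression is not an event.

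A reader might go further and infer that a trial passing with 4 successes would probably owe its result to responses that vanish with the steroid. That would apply the thalidomide share to every success, including those met after prednisone ended, and would look only at the narrowest pass. The documents support neither step. A reader might also point to the 19% response rate on prednisone plus placebo in the randomized study. No durations are given for that arm, so those responses cannot be taken as transient. What each drug contributes is a separate question.

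**Conclusion.** The point holds as a gap in reporting, not as a fault in the endpoint or the decision rule. A response met on prednisone and later lost counts in full, and nothing planned shows how often that happens. The true share is unknown. If 62% to 80% of all successes are kept, a 20% best-response rate corresponds to about 12% to 16% still responding at the end of cycle 6, or roughly 5 to 6 subjects where 7 were counted. The range depends on that assumed share. The censoring point rests on duration of response being applied as written in section 5.3.3. The documents do not support saying that the go rule is invalid or that most successes would be lost.

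**What to change.** Keep the endpoint, boundaries, significance level and power. In section 5.3.3, for the combination cohort:

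- **Add a pre-specified estimate with a confidence interval:** the proportion of evaluable subjects, with the same denominator as the primary rate, who are in CR, PR or CI at the end-of-cycle-6 visit. That is about 84 days after scheduled prednisone ended, within the ±7-day visit window.
- **Count subjects off treatment or without an assessment as not in response**, and list the reason (loss of response, toxicity, other), so that relapse and dropout are not mixed.
- **Split the successes** into first met in cycles 1–3 and kept, first met in cycles 1–3 and lost, and first met in cycles 4–6.
- **Count loss of response, as well as progression, as the end of response** in duration of response.
- **Report these figures beside the primary rate** in any recommendation for further testing.

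The cost is about a paragraph. Section 3.1 already provides visits at least every 28 days and a return visit at the end of cycle 6; Appendix M, which is not in the supplied text, should be checked to confirm that response is assessed then. The estimate will be imprecise: 5 of 37 is 13.5%, with an exact 95% interval of 4.5% to 28.8%. It should be presented as descriptive. The downside is a second, less favourable figure beside the headline rate.

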2.2.2. Secondary Endpoints

- Duration of response
- Time to response
- Best overall response as determined by International Working Group Criteria over the first 12 cycles (336 days) of study treatment
- Cytogenetic response in subjects with a baseline abnormality
- Molecular response (JAK2^{V617F} mutation burden) in peripheral blood in mutation positive subjects
- Bone marrow fibrosis improvement
- Quality of Life (QoL) assessments [the four components (Physical, Social/Family, Emotional and Functional Well-Being) and total of the 27-item FACT-G, together with the 13-item fatigue subscale, the total of the Additional Concerns, and a Likert Pain Scale for splenic pain.

3. INVESTIGATIONAL PLAN

3.1. Overall design

CC-4047 is a phase 2, prospective, open-label study to determine the efficacy and safety of CC-4047 at a 0.5 mg dose, in combination with prednisone, to study further in subjects with primary, post polycythemia vera, or post essential thrombocythemia myelofibrosis

Screening:

Potential subjects will enter screening and be evaluated for the inclusion and exclusion criteria for the Treatment Period of this study. The screening period will not last more than 28 days. The assessments and procedures that will be performed during screening are outlined in Appendix M: Schedule of Events. Screening assessments will include an informed consent, medical history, review of prior medications, complete physical exam, ECOG performance status assessment, complete blood count (CBC) with differential, serum chemistries, urinalysis, thyroid function tests, 12-lead ECG, bone marrow biopsy and aspirate to confirm diagnosis and for standard cytogenetics, JAK2 mutation (by quantitative polymerase chain reaction [PCR], and PCR or fluorescent in situ hybridization (FISH) for bcr/abl, spleen and/or liver (if spleen is absent) measurements, and QoL Assessments.

Females of reproductive potential¹ must adhere to the scheduled pregnancy testing as required in the POMALYST REMSTM program. All study participants must be registered into the mandatory POMALYST REMSTM program, and be willing and able to comply with the requirements of the POMALYST REMSTM program.

Before starting study drug:

Subjects must follow pregnancy testing requirements as outlined in the POMALYST REMS TM program.

Treatment Period:

Subjects meeting all inclusion and exclusion criteria will receive 0.5mg CC-4047. Prednisone will be given during first 3 cycles of therapy. It will be dosed orally at the dose of 30 mg/day during cycle 1, 15 mg/day during cycle 2, and 15 mg every other day during cycle 3, and then it will be discontinued. Prednisone will be used from commercially available supplies.

Subjects will remain on study treatment in the Treatment Period in the absence of disease progression or toxicity warranting discontinuation of therapy. Twenty-eight days is considered one cycle of therapy. Subjects may be taken off study at 6 months if there is no response, however, they should continue to be followed until disease progression or initiation of an alternate therapy.

¹ A female of childbearing potential is a sexually mature woman who: 1) has not undergone a hysterectomy or bilateral oophorectomy; or 2) has not been naturally postmenopausal for at least 24 consecutive months (i.e., has had menses at any time in the preceding 24 consecutive months).

Study assessments and serial measurements of safety and efficacy will be performed as outlined in Appendix M: Schedule of Assessments. All scheduled visits will have a ± 3 -day window unless otherwise stated. Beginning with Cycle 6 scheduled visits will have a ± 7 -day window.

CBCs will be monitored weekly for the first 56 days of study treatment and then, at minimum, every 28 days. Study visits will occur at least every 28 days. Study visits should occur whether or not study drug has been interrupted for an adverse event. Repeat bone marrow aspirate, biopsy and cytogenetic studies will be performed to confirm a complete response and when clinically indicated. Cytogenetic analysis may be performed on the peripheral blood if necessary. Patients who have been on the study for at least 3 cycles and had no grade 3 or 4 toxicity, will be allowed to return to MD Anderson at the end of Cycle 6, then subsequently every 6 cycles. In this case mandatory monthly visits will be done at the local referring doctor's office, and will also include phone contact by the study staff.

Pregnancy Testing

Patients must follow pregnancy testing requirements as outlined in the POMALYST REMSTM program.

